Rather than an alternative medium for implementation of existing interventions designed for in-person contact, social media may be a true 'game changer'^{74,76,77,121,122} to engage hard to reach individuals. While many online behavioral interventions exist, including some that use social media,¹⁶⁹ ours will be the first to use social media to facilitate uptake of a biomedical intervention. E-PrEP will connect the target population (YMCSM) to a new prevention tool (PrEP) through rapid linkage to medical care, accelerating diffusion of PrEP. Given the paucity of data regarding social media-based interventions to change health-related behavior, E-PrEP may have a marked impact on future bio-behavioral interventions, especially those that include diffusion of innovation.

Social media offers the power of scale and efficiency for large potential impact, even with relatively low intensity interventions.^{77,109,122} Similarly, PrEP, if widely adopted in high-risk populations and offered with behavioral interventions, could markedly decrease HIV infection rates. Social media-based, peer-led approaches like E-PrEP could be used to enhance efforts by community based and other organizations that employ internet-assisted or peer-outreach strategies to improve health.⁷⁶

Aims: To test the feasibility and preliminary efficacy of E-PrEP for increasing PrEP adoption in a cluster-randomized controlled trial.

Methods

Participants: The 16-20 peers will be randomized 1:1 to either E-PrEP or BxNow (control condition). They will then recruit n=240 total participants (120 for E-PrEP and 120 to BxNow). Each Peer will recruit approximately n=15 participants.

Inclusion criteria: Male or trans individuals; Ages 18-29; Have had unprotected anal sex with a male partner in the prior 12 months; Fluent in English or Spanish; Are HIV negative or unknown status (self-report); Identify as Black and/or Latino

Exclusion criteria: YMCSM or trans individuals who do not consent/assent to study; Are currently taking PrEP for HIV prevention, not currently using at least one of 3 social media sites that will be used for the E-PrEP intervention (e.g. not using Facebook, Twitter, Tumblr).

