1. <https://www.qualtrics.com/support/survey-platform/survey-module/survey-options/survey-protection/#PreventingRespondentsFromTakingYourSurveyMoreThanOnce>

Furthermore, we will download the raw data and store it in a password protected *and* encrypted file on the office computer of [name]. Only the PIs and research study staff will have access to the full data-set.

Analytic Plan: Our *primary outcome* will be *intention to use PrEP*,⁸³ which we consider a predictor of subsequent use,¹⁴² and will be measured using a Likert scale. We will use ‘intention’ as a proxy given the low likelihood of actual PrEP use.^{83,132,143} *Secondary outcomes* will be PrEP use, knowledge,¹⁴³ perceptions about PrEP¹³⁴ and HIV testing- and risk-behaviors.¹⁴⁴ *Covariates*^{80,81,143,145-148} will include access to medical care (including HIV/STI testing), sexual orientation, HIV and PrEP related stigma, substance use, sociodemographic factors,¹⁴⁴ social media engagement and network data,^{149,169} and perceived affinity to the referring Peer.¹⁵⁰ First, we will compare groups for equivalence at baseline, using chi-square or t-tests as appropriate. In addition, we will determine whether subgroups (e.g., grouped by number of social media sites joined, social media platform(s) used, peer referent, race/ethnicity, and sexual orientation) differ with respect to the primary and secondary outcomes. Relevant differences will be used as covariates in subsequent models. At each time point, we will examine change in our primary outcome variable (*intention to use PrEP*) by using a traditional two-sample test of proportions. To compare differences in outcomes between arms over time, we will use

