repeated measures mixed-effects logistic and linear models, with the treatment arm as a fixed-effect, Peers as a random-effect, and time (as a linear term) as an independent variable. We will also look at residual plots to determine if we need to include non-linear terms for time. Next, we will use hierarchical models to examine the role of secondary outcomes as potential mediators of change over time, e.g. are there differences by condition in PrEP knowledge or perceptions that account for differences in intentions. Finally, we will assess the impact of the exposure arm (E-PrEP or BxNow) and selected covariates (significant in the bivariate analysis at $p < 0.1$) on the primary and secondary outcomes using mixed-effects models. We will also assess the impact of online process and engagement variables on outcomes. To overcome possible limitations due to intra-cluster correlations, we will include a modified sensitivity analysis that examines outcomes in relation to participants' network size and perceived affinity to the Peers. To test *feasibility*, we will assess online process measures, including participation rate (# of individuals screening eligible and then ultimately joining the study), engagement activity (e.g. time spent viewing posted videos, # of responses posted to questions, participation in polls, etc.), and retention (# of participants actively 'leaving' or 'un-joining' a social media study site and # of respondents to follow-up assessments).

Power Analysis: The primary purpose of this study is to test feasibility and to obtain an effect size estimate for a future R01 application. We estimate that a sample size of 220, accounting for up to 20% attrition¹⁰⁶ will provide 80% power to detect an effect size of 20% in E-PrEP vs. 5% in BxNow in the proportion of participants indicating '*intention to use PrEP*' at 6 weeks, with a two-sided $\alpha < .05$. We will also have adequate power to detect a smaller effect size at 12 weeks because of our repeated measures design. This conservative effect size estimate is reasonable, given the novelty of the proposed intervention, the absence of other studies assessing uptake of a biomedical tool in YMSM, and the results of other studies assessing potential interest in PrEP.⁸³

Procedures outlined below have been guided by [name] (Consultant), and by [name] (Consultant), who has extensive experience in conducting online survey and intervention studies with vulnerable populations including MSM.

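### Intention to use PrEP is measured on a Likert scale but tested and powered as a proportion, with no definition of which responses count and no primary model named

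*Combined protocol and SAP*

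**What the plan says.** The Analytic Plan names intention to use PrEP as the primary outcome, "and will be measured using a Likert scale". The next steps use a yes/no form of it:

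- **Time-point test (Analytic Plan).** The arms are compared "by using a traditional two-sample test of proportions". No adjustment for Peer or for the baseline response is attached to this test.
- **Power Analysis.** The effect is expressed "in the proportion of participants indicating" intention. The stated sample "will provide 80% power to detect an effect size of 20% in E-PrEP vs. 5% in BxNow" at 6 weeks, two-sided at 0.05.
- **Comparison over time (Analytic Plan).** The plan names "repeated measures mixed-effects logistic and linear models, with the treatment arm as a fixed-effect", with Peers as a random effect. It does not say which of the two models goes with which outcome.

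No section gives the wording of the item, the number of scale points, or the responses that count as intention. Table 2 (Data Collection) shows that intention is collected at weeks 0, 6, 12 and 36+, so a baseline score will exist for each participant. The Power Analysis gives the purpose as feasibility plus an effect size for a later grant application.

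**The concern.** Two things are left open. First, an ordered item has as many possible yes/no versions as it has gaps between categories. Unless one is fixed in advance, several primary tests are available, and the stated 5% error rate holds only for a cut chosen without sight of the data. The unassigned logistic and linear models add a further choice. Because the trial is meant to supply an effect size, a favourable cut would also carry an inflated estimate into the next trial's planning.

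Second, the stated 6-week test uses neither the ordering of the responses, nor the T1 score, nor the Peer structure. All three are available at no extra cost, in a trial that randomises only 16–20 Peers.

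**Working it through.** **Inputs from the documents.** 20% versus 5%; two-sided 0.05; 80% power; 220 in total with up to 20% attrition (Power Analysis); 1:1 allocation of Peers (Methods, Participants). **Assumed,** because the documents are silent: a 5-point item, the response distributions below, and independent participants.

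**1. The plan's own figure.** With mean proportion 0.125:

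n = [1.960·√(2·0.125·0.875) + 0.842·√(0.20·0.80 + 0.05·0.95)]² / 0.15² = (0.917 + 0.383)² / 0.0225 ≈ 75.1, so 76 per arm.

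With the continuity correction: (75.1/4)·[1 + √(1 + 4/(75.1·0.15))]² ≈ 88 per arm. Then 2·88 = 176, and 176/0.80 = 220. The stated figure reproduces exactly, so the design treats intention as binary.

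**2. Error rate if the cut is chosen afterwards.** I simulated 40,000 null trials with 88 per arm. The pooled two-proportion test was run at each cut, and a trial was counted as positive if any candidate cut had |z| > 1.96.

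| Assumed distribution, lowest to highest (%) | Top-one or top-two cut | All four cuts |
|---|---|---|
| 35/25/20/15/5 | 8.6% | 15.8% |
| 20/20/30/25/5 | 8.9% | 16.3% |
| 60/20/10/5/5 | 7.7% | 14.6% |
| 20/20/20/20/20 | 9.0% | 15.6% |

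Repeat runs reached 16.8%. A uniform 7-point item with six cuts gives about 20%. The inflation is smaller when responses pile up at the bottom of the scale, and falls further if the pile-up is more extreme.

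**3. Cost of cutting if the effect shifts the whole scale.** A latent-normal shift that turns 5% into 20% is 1.645 − 0.842 = 0.803 SD.

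- Full scale: n = 2·(1.960 + 0.842)²/0.803² ≈ 24.3, so 25 per arm.
- As a proportion at the planned cut: 76 per arm (both figures without continuity correction). The loss is 1 − 25/76 = 67%.
- Mean scores on four assumed 5-point distributions (the first three above and 80/5/5/5/5) need about 26 to 38 per arm. At 38 the loss is 1 − 38/76 = 50%.
- Same shift with 20–40% of controls above the cut: 40 to 43 per arm, a loss of 1 − 25/40 = 38% to 1 − 25/43 = 42%.
- Smallest possible loss, at a median cut against an ideal continuous scale: 1 − 2/π = 36%.

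**4. Cost of not cutting if the effect is only a move into the top category.** Change 35/25/20/15/5 to 35/25/20/0/20. The mean moves by 0.15 and the variances are 1.51 and 2.1475. A mean-score test then needs (1.960 + 0.842)²·(1.51 + 2.1475)/0.15² ≈ 1,276 per arm. For 20/20/30/25/5 moving to 20/20/30/10/20 it needs about 1,143. The top-category proportion still needs 76.

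**5. Power at the planned effect.** The planned odds ratio is (0.20/0.80)/(0.05/0.95) = 4.75. With 88 per arm and no continuity correction, the top-category test has about 88% power by simulation (86% by the normal formula). A full-scale rank test has about 100% under a common odds ratio. Under a move confined to the top category, the full-scale test has about 7–19% and the top-category test keeps 88%.

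**The case against.** There are four good arguments for the plan as it stands.

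- **A proportion is a legitimate target.** It is easy to interpret and suits the planning of a later trial. At the planned 20% versus 5%, and with independent participants, it is adequately powered (step 5). This stands.
- **The full scale is not uniformly better.** Turning people close to adopting PrEP into definite intenders is a plausible way for this intervention to work, and in that case the full-scale test is far weaker (step 4). This stands, and it is why the proportion should stay in the plan at a fixed cut.
- **A full-scale analysis is not excluded.** Linear mixed models are listed beside logistic ones. This is correct, but neither is assigned to intention or called primary, so it adds to the open choices.
- **This is a pilot.** That lowers the weight of a formal error rate. It does not help the effect size estimate, which is a stated product of the trial.

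The plan also cites outside sources for the intention measure. They cannot be checked here, and the plan does not say that it adopts a cut-off from them.

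A reader might infer that dichotomising discards most of the information. The documents do not support that, because they give no Likert distribution and the loss runs from none to about two thirds depending on how the intervention acts. A contrast of about 20% power for the top category against 71–73% for the full scale can be produced, but only at an odds ratio of 2. That moves 5% to just 9.5% (0.0526·2 = 0.105; 0.105/1.105 = 0.095) and is not the planned effect.

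**Conclusion.** The point holds in a limited form. The outcome is ordinal, and its time-point test and sample size are binary. The defining responses are not stated, and the primary model is not named. The effect of an open cut-off on the error rate does not depend on how the intervention works: about 8–9% with two candidate cuts and 15–17% with four, against a nominal 5%. It does depend on someone choosing the cut after seeing the data. The documents leave room for that but do not show any intention to do so.

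The efficiency gain from the full scale is conditional: roughly 36–67% of the information under a whole-scale shift, and none if the effect sits in the top category. All figures assume 88 evaluable participants per arm and no clustering. The stated 220 likewise contains no clustering allowance, which is a separate matter. This is a cheap improvement that should be made; it does not invalidate the design.

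**What to change.** Before any T2 data are opened, amend the Analytic Plan to:

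1. State the intention item, its number of points, and one cut-off that defines intention.
2. Name one primary 6-week analysis in place of the two-sample test of proportions: a mixed model of the full Likert score with a Peer random effect and the T1 intention score as covariate. Choose either a cumulative-logit model or the linear model already listed, and say which.
3. Report the two proportions and their difference at the fixed cut-off as the supportive effect size for the later trial.
4. Say which of the logistic and linear models applies to each remaining outcome.

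The cost is wording only; Table 2 already schedules the data. The price is that the primary estimate rests on a common-shift (proportional-odds) assumption, and it loses power if the effect is confined to the top category. The pre-fixed proportion covers that case. How the chosen model behaves with 8–10 Peers per arm was not examined here and should be checked when it is specified.

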individual and members of their networks and our intervention capitalizes on this point. While biases in online recruitment for this population are unknown at this time, our recruitment strategy may potentially be less biased than studies involving in-person recruitment. Strategies now exist that allow us to use social media for instantaneous display of a recruitment post or message to all members of the Peers' online network on a given social media platform. This potentially provides opportunities for a more diverse sample, than might be had if it were based on in-person recruitment approaches – as in-person approaches selects for participants who more frequently interact with a given recruiter, an issue that is less important online. Regardless, we will pay close attention to this issue, as best practices for online recruitment and sampling strategies are constantly evolving.^{130,135,136,155,165-167} Ongoing discussions with [name] (consultant) and staying current on this topic through ongoing literature review and conference attendance will inform changes, if any, that will be made to our proposed approach to reduce potential bias. Additionally, we (PI) will provide thorough training to the Peers in how to target YMCSM. The Peers will also represent diverse YMCSM communities in the Bronx, further aiding in recruitment of a broad sample of 18-29yo Bronx YMCSM. In addition to implementing best practices for reducing bias in online recruitment, collection of key sociodemographic data will enable us to compare the groups at baseline.^{60,119,131,135,138-140,166,168}

10. **Risk Compensation:** The E-PrEP intervention will include substantive education and discussion around risk reduction strategies and make it very clear that PrEP has been designed to be used with these other behavioral strategies to reduce HIV acquisition risk and does not provide complete protection by itself. We will monitor for evidence of risk compensation by collecting data in our assessment surveys about HIV risk behaviors and evaluate participants' HIV risk behaviors in relation to PrEP intention and use. At the conclusion of the trial, we will attempt to link any individual showing evidence of risk compensation in further education and counseling with online and in-person resources.

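### Baseline equivalence is judged by chi-square and t-tests that ignore Peer: a non-significant result cannot show it, and a significant one is unreliable

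*Combined protocol and SAP*

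**What the plan says.** The Analytic Plan opens its analysis with this step: "First, we will compare groups for equivalence at baseline, using chi-square or t-tests as appropriate". It gives no test level, margin, confidence interval or threshold for a standardised difference, and does not mention Peer at this step.

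The plan next looks for subgroup differences in the outcomes and then says: "Relevant differences will be used as covariates in subsequent models". Relevance is not defined. It is also not clear whether the sentence covers the baseline comparison, the subgroup comparison or both. A second route lets covariates into the final mixed-effects models if they reach p < 0.1 in bivariate analysis. Intention at each time point is examined "using a traditional two-sample test of proportions", with no adjustment stated. The covariate list names access to care, sexual orientation, stigma, substance use, sociodemographic factors, social media engagement, network data and affinity to the Peer. It does not name baseline intention, although Table 2 (Data Collection) shows intention measured at week 0.

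Section I.5, item 9, on a possibly biased sample, ends by noting that "collection of key sociodemographic data will enable us to compare the groups at baseline".

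**The concern.** The stated aim is equivalence, but the stated method can only reject sameness. Failing to reject at this sample size is weak evidence that the arms are alike.

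The design makes this matter more than usual. Peers are randomised first and then recruit from their own networks to a condition already assigned. Participants who come through Facebook advertisements are allocated at random among the Peers who are struggling to recruit. Baseline differences can therefore come from differential recruitment as well as chance, so comparing the arms is a sensible thing to do. Participants of one Peer may also resemble one another, and a chi-square or t-test that treats all 240 as independent then has the wrong error rate.

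At stake is what the trial may say about comparability, and how far readers trust the week-6 difference. The Power Analysis section wants that difference as the effect-size estimate for a later application.

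**Working it through.** **Inputs from the documents.** 120 per arm, 16 to 20 Peers and about 15 participants per Peer (Participants). Two-sided 5% level and a planned contrast of 20% vs 5%, or 15 points (Power Analysis).

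**Assumptions.** The 5% level for the baseline tests, the baseline rates and SD gaps, the intracluster correlation (ICC), and the strength of any covariate. The documents give none of these.

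1. **The plan's own figure.** It claims "80% power to detect an effect size of 20% in E-PrEP vs. 5% in BxNow" from "a sample size of 220, accounting for up to 20% attrition". The two-proportion formula gives 75.1 per arm. With continuity correction this becomes 75.1/4 × (1 + √(1 + 4/(75.1 × 0.15)))² = 87.9, so 88 per arm and 176 in total. Then 176/0.80 = 220. The figure reproduces exactly, with no allowance for clustering. It is not affected by this point.

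2. **How often the tests miss a true gap (no clustering).** For proportions I enumerated the two binomials exactly and applied the pooled z (chi-square) test. For means I used the non-central t with 238 df and non-centrality d√(120/2).

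| True gap | P(non-significant) |
|---|---|
| 5% vs 10% | 0.675 (0.778 with continuity correction) |
| 20% vs 30% | 0.566 |
| 40% vs 50% | 0.665 |
| 0.20 SD (non-centrality 1.549) | 0.661 |
| 0.25 SD (non-centrality 1.936) | 0.512 |

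3. **Largest observed gap that stays non-significant.** 6/120 vs 14/120 (5.0% vs 11.7%, 6.7 points) gives z = 1.87. 54/120 vs 69/120 (45.0% vs 57.5%, 12.5 points) gives z = 1.94. For a continuous measure it is 1.96 × √(2/120) = 0.253 SD.

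4. **How often the tests flag when there is no systematic difference (clustering present).** With m per Peer, the variance of the arm difference is inflated by DE = 1 + (m − 1) × ICC, and the false-flag rate is 2Φ(−1.96/√DE).

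| ICC | DE, m = 15 | False-flag rate | DE, m = 12 (20 Peers) | False-flag rate |
|---|---|---|---|---|
| 0.02 | 1.28 | 8.3% | 1.22 | 7.6% |
| 0.05 | 1.70 | 13.3% | 1.55 | 11.6% |
| 0.10 | 2.40 | 20.6% | 2.10 | 17.6% |

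A simulation of 16 Peers with 15 participants each and a 50% covariate agrees: 7.6%, 12.7% and 19.9% for m = 15.

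5. **Over-flagging does not cure the missing.** Take 5% vs 10% by normal approximation. The pooled SE is √(2 × 0.075 × 0.925/120) = 0.0340, so the critical gap is 0.0666. The true SE is 0.0339 × √DE. The chance of a non-significant result is 69% at ICC 0, 64% at 0.05 and 61% at 0.10.

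6. **What an interval that accounts for Peer would show.** Half-width = 1.96 × √((2/120) × DE): 0.253 SD at ICC 0, 0.286 at 0.02, 0.330 at 0.05 and 0.392 at 0.10.

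7. **Scale of a possible effect on the estimate (illustration only).** One covariate with a 10 to 12 point imbalance, whose levels differ by an assumed 10 to 30 points in outcome, shifts an unadjusted contrast by 0.10 × 0.10 = 1.0 to 0.12 × 0.30 = 3.6 points, or 7% to 24% of 15. A 6.7-point gap in baseline intention (assuming a rate near 5%) would be 6.7/15 = 44% of the planned effect if carried forward in full, and about 13% if 30% were carried forward.

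**The case against.** The strongest reply is that the sentence is loosely worded, does not set up an equivalence claim, and is not the last safeguard. The comparison can feed covariate selection, the p < 0.1 screen is a second way in, and the mixed models carry a random effect for Peer. Intention is measured at week 0 and followed over time, so a baseline gap in it would be visible. For a measured variable, bias comes from the imbalance in the enrolled sample, which will be known whatever the p-value. The study is also a pilot.

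Much of this stands, and it rules out three stronger readings that a reader might infer:

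- That the trial will declare its arms equivalent and leave imbalances unadjusted. No text says that a non-significant test bars adjustment or will be reported as equivalence.
- That the week-6 effect will be biased by a known amount. Step 7 rests wholly on assumed prognostic strength and carry-over.
- That section I.5, item 9, relies on this comparison as its answer to a biased sample. The item lists consultant advice, literature review, Peer training and diverse Peers first, and adds the baseline comparison last.

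The reply does not rescue the test itself. If relevance comes to mean statistical significance, adjustment inherits the error rates above. The p < 0.1 screen is data-driven and is stated only for the final models. The time-point tests state no adjustment. A Peer random effect allows for correlation but does not remove a systematic difference between arms that arises in recruitment.

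**Conclusion.** The point holds as a modest one. The named tests cannot support the stated aim of equivalence, and they ignore the unit of randomisation. Without clustering they miss a true 5% vs 10% gap about 68% of the time and a 0.25 SD gap about 51%. With 15 per Peer they flag chance differences about 8% to 21% of the time over ICCs of 0.02 to 0.10, instead of 5%. These figures assume a two-sided 5% level, and the rates, gaps and ICCs are assumed too. The conclusion about non-significance does not depend on any single one of them. The conclusion about over-flagging needs some correlation within Peers, which recruitment from personal networks makes plausible but the documents do not quantify.

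The result limits what the trial may conclude about baseline comparability. It does not show that the effect estimate will be distorted.

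**What to change.** Replace the baseline sentence in the Analytic Plan with wording such as:

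*Baseline comparability will be described by the between-arm difference (standardised, and in percentage points for T1 intention) with a 95% confidence interval that accounts for Peer. A non-significant difference will not be taken as evidence of equivalence. Baseline p-values will not decide adjustment. Models of post-baseline outcomes will include T1 intention and the following baseline covariates whatever the baseline comparison shows: [short list chosen now from those already named].*

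Then remove or define the relevance criterion, and drop the p < 0.1 screen as the gate for these covariates. If the test of proportions at each time point is kept, label it unadjusted and show the adjusted estimate beside it. The description alone would not remove any bias; the fixed adjustment is the part that deals with measured imbalance.

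A formal equivalence test is not a practical alternative. Two one-sided 5% tests with about 80% power and no true difference need 2 × (1.645 + 1.282)²/0.20² ≈ 429 per arm for a 0.20 SD margin, and about 275 for 0.25 SD, before clustering.

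The cost is a few sentences and one table column, using T1 data already collected. The trial can no longer say that the arms were equivalent at baseline, and a few degrees of freedom are used. The list should be short: at the planned rates, 120 per arm gives only 24 + 6 = 30 participants with intention at week 6, before attrition.
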